8.1.3 Assessment of Adverse Events by the Investigator

The Investigator will assess the severity (intensity) of each adverse event and will also categorize each adverse event as to its potential relationship to study drug using the categories of “yes” or “no.”

Assessment of Severity:

The severity of all adverse events should be graded according to the Common Terminology Criteria for Adverse Events (CTCAE) v4.03. These criteria can be found at <http://ctep.cancer.gov/reporting/ctc.html>. For those adverse events not listed in the CTCAE, the following grading system should be used:

- Mild (CTCAE Grade 1): Transient symptoms, awareness of sign/symptom, but easily tolerated and no interference with patient’s daily activities

- Moderate (CTCAE Grade 2): Marked signs/symptoms that interfere with patient's usual activities, but still acceptable
- Severe (CTCAE Grade 3): Incapacitating signs/symptoms which cause considerable interference with the patient's daily activities, unacceptable
- Life-threatening (CTCAE Grade 4): Life threatening or disabling adverse event
- Death (CTCAE Grade 5): Death-related adverse event

Causality Assessment:

The relationship of an adverse event to the administration of the study drug is to be assessed according to the following definitions:

No (unrelated, not related, no relation) – The time course between the administration of study drug and the occurrence or worsening of the adverse event rules out a causal relationship and another cause (concomitant drugs, therapies, complications, etc.) is suspected.

Yes (related) – The time course between the administration of study drug and the occurrence or worsening of the adverse event is consistent with a causal relationship and no other cause (concomitant drugs, therapies, complications, etc.) can be identified.

The definition implies a reasonable possibility of a causal relationship between the event and the study drug. This means that there are facts (evidence) or arguments to suggest a causal relationship.

The following factors should also be considered:

- The temporal sequence from study drug administration-
 - The event should occur after the study drug is given. The length of time from study drug exposure to event should be evaluated in the clinical context of the event
- Underlying, concomitant, intercurrent diseases-

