### **7 STATISTICAL METHODOLOGY**

#### **7.1 General Considerations**

##### **7.1.1 *Summary Statistics***

Summary statistics will be presented in total. For continuous variables, the number of observations (n), mean, standard deviation, median, minimum, and maximum will be provided. For categorical variables, the frequency and percentage in each category will be displayed.

For summary statistics, the mean and median will be displayed to one decimal place greater than the original value and the measure of variability (e.g. standard deviation) will be displayed to two decimal places greater than the original value.

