### **7.6.2 Clinical Laboratory Tests**

Central laboratory test results (chemistry, hematology, coagulation, and urinalysis) at each scheduled visit and change from baseline will be summarized with descriptive statistics.

Shift tables from baseline to each scheduled post-baseline visit will be provided for selected chemistry parameters (ALT, AST, ALP, Total Bilirubin, Creatinine, and Creatinine Kinase) and hematology parameters (Hematocrit, Hemoglobin, Platelets, White blood cell count and differential). For chemistry parameters, the following categories will be used: < the lower limit

of normal (LLN), normal,  $>\text{ULN}$  to  $\leq 2 \times \text{ULN}$ ,  $>2 \times \text{ULN}$  to  $\leq 3 \times \text{ULN}$ ,  $>3 \times \text{ULN}$  to  $\leq 5 \times \text{ULN}$ ,  $>5 \times \text{ULN}$ , and missing. For hematology parameters, the following categories will be used: low, normal, high, and missing.

The number and percentage of patients with the following potentially clinically significant abnormal liver function tests at any post-baseline visit will be summarized:

- $\text{ALT} \geq 3 \times \text{ULN}$
- $\text{ALT} \geq 5 \times \text{ULN}$
- $\text{ALT} \geq 10 \times \text{ULN}$
- $\text{AST} \geq 3 \times \text{ULN}$
- $\text{AST} \geq 5 \times \text{ULN}$
- $\text{AST} \geq 10 \times \text{ULN}$
- $\text{ALT}$  or  $\text{AST} \geq 3 \times \text{ULN}$
- Total Bilirubin  $>1.5 \times \text{ULN}$
- Total Bilirubin  $>2 \times \text{ULN}$
- $\text{ALP} \geq 1.5 \times \text{ULN}$
- $\text{ALP} \geq 2 \times \text{ULN}$
- $\text{ALT}$  or  $\text{AST} \geq 3 \times \text{ULN}$  and Total Bilirubin  $>1.5 \times \text{ULN}$
- $\text{ALT}$  or  $\text{AST} \geq 3 \times \text{ULN}$  and Total Bilirubin  $>2 \times \text{ULN}$
- Potential Hy's Law cases:  $\text{ALT}$  or  $\text{AST} \geq 3 \times \text{ULN}$  and Total Bilirubin  $>2 \times \text{ULN}$ , and  $\text{ALP} \leq 2 \times \text{ULN}$

A listing of patients with any post-baseline clinically significant abnormal liver function tests will be presented.

All clinical laboratory data will be listed. Values outside the normal ranges will be flagged.

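### The haematology shift tables have one undivided low category, so no planned table objectively counts patients by depth of cytopenia or by worsening from a low baseline (minor)

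*SAP*

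**What the plan says.** SAP 7.6.2 plans several laboratory outputs.

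- **Shift tables.** "Shift tables from baseline to each scheduled post-baseline visit will be provided for selected chemistry parameters", and likewise for hematocrit, hemoglobin, platelets, and white cells with differential. For chemistry the sentence starting "For chemistry parameters, the following categories will be used" gives one category below the lower limit, one for normal, four bands above the upper limit (the last being >5 x ULN), and missing. For haematology: "For hematology parameters, the following categories will be used: low, normal, high, and missing".
- **Threshold counts.** "The number and percentage of patients with the following potentially clinically significant abnormal liver function tests at any post-baseline visit will be summarized". Fourteen criteria follow, all built from ALT, AST, total bilirubin and ALP. There is no equivalent for blood counts.
- **Continuous summaries.** "Central laboratory test results (chemistry, hematology, coagulation, and urinalysis) at each scheduled visit and change from baseline will be summarized with descriptive statistics". SAP 7.1.1 fixes the statistics: "For continuous variables, the number of observations (n), mean, standard deviation, median, minimum, and maximum will be provided".
- **Listings.** "All clinical laboratory data will be listed. Values outside the normal ranges will be flagged".

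Adverse events are a second route. Protocol 8.1 makes a clinically significant laboratory abnormality reportable if it arises during the study, or if it was there at Screening and gets significantly worse. An abnormality judged not clinically significant is not an adverse event. Protocol 8.1.3 gives the scale: "The severity of all adverse events should be graded according to the Common Terminology Criteria for Adverse Events (CTCAE) v4.03". SAP 7.6.1 tabulates treatment-emergent events by worst grade.

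**The concern.** The toxicity of interest for blood counts is usually a fall, and below the lower limit the shift table has no resolution at all. The chemistry table, by contrast, is finely divided in its direction of interest.

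Patients with low counts can enter. Protocol 4.2 sets no numerical haematology limit. Exclusion criterion 12 only lets the investigator exclude a laboratory abnormality thought to carry unacceptable risk or to interfere with assessments. For a patient who enters low, a further fall cannot leave the low-to-low cell, whatever its size.

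Safety is part of the primary objective (Protocol 2.1) and there is no control arm (Protocol 3.1), so each patient's own baseline is the main internal reference. A reader of the study report could take a low-to-low entry to mean a stable count.

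**Working it through.** The plan states no figure for this point, so there is nothing to reproduce. The check has four steps.

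**1. Apply the category rule.** The platelet reference range of 150 to 400 x10^9/L is assumed; it is not in the documents. The pairs are illustrative.

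| Baseline | Post-baseline | Change | Shift-table cell |
|---|---|---|---|
| 140 | 120 | -20 | low to low |
| 140 | 20 | -120 | low to low |
| 80 | 15 | -65 | low to low |
| 200 | 140 | -60 | normal to low |
| 200 | 20 | -180 | normal to low |

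The first three pairs share one cell and the last two share another. So depth is lost for patients who start normal as well as for those who start low. Other limits would move the boundary but would not divide the low category.

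**2. See what the continuous summary adds.** Suppose one of 15 patients falls from 80 to 15 and the other 14 changes average zero. The mean change is -65/15 = -4.3. In an invented set of 15 in which the other 14 patients moved by at most 20 either way, the mean change was -3.3 and the median +2.0. The printed minimum value was 15 and the minimum change -65. The extreme patient is therefore visible in the minima. But a minimum change of -65 could equally be 215 to 150, which stays normal under the assumed range. A minimum also describes one patient and does not say how many worsened.

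**3. Set the planned outputs side by side.**

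| Output | Tied to own baseline | Shows depth below the limit | Counts patients | Free of clinical-significance judgement |
|---|---|---|---|---|
| Haematology shift table | yes | no | yes | yes |
| By-visit values | no | through the minimum only | no | yes |
| Change from baseline | yes | no (size of change, not level) | no | yes |
| Flagged listings | yes, by reading | yes, by reading | no | yes |
| Adverse events by worst grade | no baseline grade shown | yes | yes | no |

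No row has all four properties. The listing flag also does not mark worsening, because a patient who is low throughout is flagged throughout.

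**4. Ask whether low baselines are likely to occur at all.** The documents give no baseline haematology. Assume that a share p of patients start low on a given parameter, independently. The chance of at least one among 15 is 1 - (1 - p)^15. For p = 0.2 this is 1 - 0.8^15 = 0.965. For p = 0.4 it is 1 - 0.6^15 = 0.9995. For p = 0.6 it is about 1. Over this assumed range at least one such patient is likely. This says nothing about how many would worsen.

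**The case against.** The strongest reply is that this is a coherent descriptive plan for a small Phase 2 study and that the gap is one of display. With about 15 patients the listings can be read patient by patient. Values and within-patient changes are summarised with minima and maxima. Clinically significant worsening of an abnormality present at Screening is an adverse event, graded and tabulated by worst grade. The stopping rule in Protocol 8.5.1 counts related laboratory events of Grade 2 or higher, and a DSMB reviews accumulating data. The finer liver categories match the protocol's explicit liver focus (exclusion criteria 3, 6 and 7, and Appendix D), so coarser haematology categories are not an evident slip.

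Most of this stands, and it rules out several stronger readings.

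- A reader might infer that blood toxicity would go unseen. It would not: an extreme value appears in the minima and the listings and, if judged clinically significant, in the adverse event tables.
- A reader might infer that the shift table is the only output linking baseline to later values. Change from baseline also does so. The shift table is the only cross-tabulation of the two.
- A reader might infer that the patients with most to lose from the drug are the ones obscured. The documents give no haematological signal for APX001; Protocol 1.2 names headache, dizziness, fatigue, nausea and vomiting.
- A reader might take the hematocrit and white-count bands of the APACHE II form as the standard for these tables. That score is a severity measure taken at Baseline (Protocol 8.9), not a toxicity scale.

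What the reply does not meet is narrower. The only planned count of patients that reflects depth runs through the investigator's view of clinical significance, in an open-label study, and it does not show the grade the patient started from.

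**Conclusion.** The point holds as a minor weakness in the safety display. Under SAP 7.6.2 a further fall from a low baseline is tabulated as no shift, and normal-to-low mixes mild with severe. No other planned table supplies an objective count of patients by depth of cytopenia or by worsening from a low baseline.

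The categorisation follows from the SAP text alone. The platelet range, the example values and the shares starting low are assumptions used only to illustrate. A reader might want the number of severe falls the table would miss. The documents do not support one, because they give neither the share of patients with low baselines nor any rate of severe worsening. Collected data and the primary efficacy analysis are unaffected.

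**What to change.** Amend SAP 7.6.2 as follows, before database lock.

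- For hemoglobin, platelets, white cells, neutrophils and lymphocytes, derive the CTCAE v4.03 grade in the decreasing direction and cross-tabulate baseline grade against grade at each scheduled post-baseline visit and at the worst post-baseline value.
- Report the number and percentage of patients who worsen by at least one grade, and of those who reach Grade 3 or higher.
- State whether unscheduled results count towards the worst value, since Protocol 8.7 allows extra tests and the existing summaries are by scheduled visit. Including them is preferable.
- Keep low, normal, high and missing for any parameter without a CTCAE scale.

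Two points need wording. The protocol applies CTCAE to adverse events, so the SAP should say that these grades are derived from laboratory values for tabulation only and do not create adverse events. The grade limits are not in either document and should be taken from the published criteria into the programming specifications.

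The cost is a short SAP change, slightly larger tables and minor programming on data already collected.

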4.4 Withdrawal Criteria

Study drug dosing may be discontinued for any of the following reasons:

- The patient withdraws consent or requests discontinuation from the study for any reason
- Occurrence of any medical condition or circumstance that exposes the patient to substantial risk and/or does not allow the patient to adhere to the requirements of the protocol
- Occurrence of significant drug-induced liver injury (DILI) [\[Appendix D\]](#)
- Any SAE, clinically significant adverse event, severe laboratory abnormality, intercurrent illness, or other medical condition that indicates to the Investigator that continued participation is not in the best interest of the patient
- Pregnancy
- Requirement of prohibited concomitant medication
- Patient failure to comply with protocol requirements or study-related procedures
- Termination of the study by the Sponsor or the regulatory authority
- Patients who discontinue study drug due to withdrawal of consent, death, or loss to follow-up will discontinue study participation. Patients who fail on study treatment and start alternative antifungals will be assessed for safety 4 weeks after stopping study medication. Patients who discontinue study drug for other reasons will enter the follow-up phase of the study.

If a patient withdraws prematurely from the study due to any of the above criteria or for any other reason, study staff should make every effort to contact the Sponsor prior to discontinuation, if possible, and to complete the full panel of assessments scheduled for the Early Termination Visit. The reason for patient withdrawal must be documented in the eCRF.

In the case of patients lost to follow-up, attempts to contact the patient must be made and documented in the patient's medical records.

Withdrawn patients will not be replaced.

The study may be discontinued for any of the following reasons: five or more subjects in study (cumulative) experience a same Grade 2 (or higher) related AE (laboratory or systemic) which is coded in the same high-level group term per MedDRA coding, throughout the duration of study; a recommendation from the DSMB based on other safety signals; lack of Investigational Product availability; inability to enroll the study; or decision by a regulatory authority or the sponsor.

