### 2.2 Study Design

This is a multicenter, open-label, non-comparative, single arm study to evaluate the efficacy and safety of APX001 for the treatment of candidemia and/or invasive candidiasis caused by *C. auris* in patients aged 18 years and over with limited antifungal treatment options. Approximately 4-6 sites will be selected from the Republic of South Africa and Panama. The Study Drug Treatment Period will be up to a maximum of 42 days (inclusive of the loading dose [Study Day 1]). There will be a Follow up Period of 4 weeks (+4 days) after EOST. The total duration of participation in the study is up to approximately 10.5 weeks (inclusive of the Screening Period [ $\leq$ 168 hours prior to Baseline]). Patients must have had *C. auris* confirmed in culture  $<$ 120 hours (for candidemia) or  $<$ 168 hours (for invasive candidiasis without candidemia) prior to qualification and dosing in the study.

Screening and Baseline procedures will be performed within no more than 120 hours (for candidemia) or 168 hours (for invasive candidiasis without candidemia) from the time that the SOC blood and/or tissue sample or aspirate/fluid positive for *C. auris* was collected, and any outstanding baseline procedures completed before the first dose of study medication.

On Study Day 1 (or over the first 24 hours if dosing starts in the evening), a 1000 mg APX001 loading dose will be administered over 3 hours by IV infusion twice daily (BID). On Study Days

2 and 3, a 600 mg APX001 maintenance dose will be administered over 3 hours by IV infusion once daily (QD). On Study Day 4 and onward, the APX001 maintenance dose will be administered as either 600 mg APX001 IV infusion QD over 3 hours or 800 mg PO QD. Patients who have completed a minimum of 3 days of IV APX001, are clinically stable as determined by the Investigator, and are able to swallow tablets, may switch from IV to PO dosing on Study Day 4 and onward. Study drug will be administered for 14 days after clearance of *Candida* organisms from the bloodstream (two consecutive negative blood cultures), and in accordance with clinical judgment as applicable for other infected sites, up a maximum of 42 days.

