Patients will be monitored by daily blood culture from signing informed consent, through dosing, during Study Drug Treatment until 2 consecutive blood cultures are negative for *Candida* spp., at EOST, and at 2 and 4 weeks after EOST, or Early Termination. For patients diagnosed with invasive candidiasis, relevant cultures, histopathology, and imaging tests to assess the site(s), extent, progress, and outcome of the *Candida* infection will be conducted as clinically indicated. All results should be recorded in the electronic Case Report Form. The management of intravascular catheters, intravascular devices, and, if applicable, any drains will be recorded, including any associated microbiology results.

Patients will be monitored for safety throughout the duration of the study. Safety assessments will include vital signs, clinical laboratory assessments (serum chemistry, hematology, coagulation, and urinalysis), physical examinations, neurological assessments (twice weekly on treatment), prior and concomitant medication reporting, and adverse event reporting. A 12-lead electrocardiogram (ECG) will be performed at Baseline (pre-dose), EOST, and 4 weeks after EOST, or Early Termination. A dilated fundoscopic examination will be performed at least once during the baseline period, which exclusively for this assessment may be up to Day 3 of the study. Follow-up fundoscopic examinations are required at EOST, and 4 weeks after EOST, or Early Termination for those patients who had positive findings up to Day 3 (or more if clinically indicated). A urine pregnancy test (for females of childbearing potential only) will be performed at Screening and Baseline (pre-dose), every 30 days during treatment if required by local regulations, at EOST, and 2 and 4 weeks after EOST, or Early Termination.

[figure not shown]
In the event of an inadequate response/failure on APX001 study treatment, the study drug may be discontinued and alternative antifungal treatment instituted.

Plasma samples for PK (APX001 [prodrug] and APX001A [active moiety]) will be collected at Baseline (pre-dose), twice weekly during Study Drug Treatment, and at EOST, 2 weeks after EOST, or Early Termination. Plasma samples for PK will be collected at the same time as samples are collected for the study's clinical laboratory assessments. Serum samples for (1,3)- $\beta$ -D-glucan levels will be collected at Baseline (pre-dose) and EOST, or Early Termination (if applicable).

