##### **6.4.5.2 Clinical Laboratory Evaluations**

Screening laboratory assessments to determine eligibility will be performed at the local laboratory and may have been collected as SOC within the previous 24 hours. Laboratory assessments collected after Screening will be sent to the central laboratory for analysis.

Clinical laboratory assessments (serum chemistry, hematology, coagulation, and urinalysis) will occur at Baseline (pre-dose), twice weekly during Study Drug Treatment, at EOST, and at 2 and 4 weeks after EOST, or Early Termination. If clinically indicated and at the discretion of the Investigator, or if a suspected adverse event is identified, clinical laboratory assessments may be conducted at any time during the study and compared to Baseline. The following is a complete list of clinical laboratory analytes.

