#### **7.4.2.5 DRC Assessments**

Reasons for EOST failure according to DRC classifications (i.e. because (i) Blood cultures and/or cultures from other sites did not become negative at EOST, (ii) *Candida* infection spread to other sites, (iii) Additional antifungals given, (iv) Patient died, (v) Patient withdrew from study but did not die, or (vi) Other), will be summarized descriptively at the EOST visit for the MITT and PP populations. Once a patient has failed treatment, they are subsequently evaluated only for survival and for relevant safety parameters.

Reasons for relapse, or other reasons for not having an outcome of sustained success at follow-up according to DRC classifications, will be summarized descriptively at 2 and 4 weeks after EOST for the MITT and PP populations. Once a patient has relapsed, or has been assessed as a non-sustained success for any reason, they are subsequently evaluated only for survival and for relevant safety parameters.

Reasons for death according to DRC classifications (i.e. Candidemia/invasive candidiasis probably contributory, candidemia/invasive candidiasis probably not contributory, or not known) will be tabulated for the MITT and PP populations.

Factors that can affect outcome, such as intravascular catheter management (timely removal of lines), will be also be summarized descriptively.

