### **7.6 Safety Assessment**

Safety data will be summarized based on the ITT/Safety Population.

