### **7.6.1 Adverse Events**

AEs will be captured from the date of informed consent through study completion. All AEs will be coded to system organ class and preferred term using the MedDRA, Version 22.0. Treatment-emergent adverse events (TEAEs) are defined as AEs that start on or after the administration of study drug.

An overview of AEs will be provided including counts and percentages of patients (and event counts) with the following:

- Any AEs;
- Any TEAEs (overall and by maximum severity);
- Any study drug-related TEAEs (overall and by maximum severity);
- Any serious AEs (SAEs);
- Any treatment-emergent SAEs (TESAEs);
- Any study drug-related treatment-emergent SAEs (TESAEs);
- Any TEAEs leading to discontinuation of study drug;
- Any study drug-related TEAEs leading to discontinuation of study drug; and
- Any AEs leading to death.

The overview of AEs will be repeated for the subsets of AEs occurring during the treatment period and AEs occurring after the treatment period in the same manner above.

The number and percentage of patients who experienced at least one TEAE will be presented by system organ class and preferred term. Drug-related TEAEs, study drug withdrawals due to TEAEs, and all SAEs will be summarized in the same manner.

Summaries will be provided by worst grade for the number and percentage of patients with TEAEs and for patients with drug-related TEAEs by system organ class and preferred term.

Although a patient may have two or more TEAEs, the patient is counted only once within a system organ class and preferred term category. The same patient may contribute to two or more preferred terms in the same system organ class category.

A list of patients who have SAEs, a list of patients who discontinue from study drug due to TEAEs, and a list of death due to AEs will be provided. All adverse events will be listed.

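### SAP 7.6.2 counts liver-threshold crossings on and after APX001 in one line, without the during/after split that SAP 7.6.1 applies to adverse events

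*SAP*

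**What the plan says.** **The count.** For each liver threshold, SAP 7.6.2 says: "The number and percentage of patients with the following potentially clinically significant abnormal liver function tests at any post-baseline visit will be summarized". The list has 14 rows: single-analyte cuts for ALT, AST, total bilirubin and ALP, an ALT-or-AST row, two aminotransferase-plus-bilirubin rows, and potential Hy's Law cases. For the denominator, SAP 7.6 says: "Safety data will be summarized based on the ITT/Safety Population".

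**When the tests are done.** SAP 6.4.5.2 schedules chemistry at Baseline, then "twice weekly during Study Drug Treatment, at EOST, and at 2 and 4 weeks after EOST, or Early Termination". SAP 2.2 adds: "There will be a Follow up Period of 4 weeks (+4 days) after EOST".

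**What patients may be taking by then.** On inadequate response, SAP 2.2 says "the study drug may be discontinued and alternative antifungal treatment instituted". Protocol 4.4 says: "Patients who fail on study treatment and start alternative antifungals will be assessed for safety 4 weeks after stopping study medication". SAP 7.4.2.5 says: "Once a patient has failed treatment, they are subsequently evaluated only for survival and for relevant safety parameters".

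**How adverse events are handled.** SAP 7.6.1 says: "The overview of AEs will be repeated for the subsets of AEs occurring during the treatment period and AEs occurring after the treatment period". Section 7.6.2 has no matching provision.

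**The concern.** The threshold count combines two or three different situations: a value reached while taking APX001, a value reached after stopping it with no other antifungal, and a value reached after stopping it and starting another antifungal. These carry different information about the drug, and the table cannot tell them apart.

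The study has one arm, so no control rate shows how many elevations late illness or other drugs would produce. Liver injury is also a stated concern of the protocol, which lists it among the reasons to stop dosing (section 4.4) and sets criteria in Appendix D. With about 15 patients, one or two late crossings visibly change a reported percentage.

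The risk runs both ways. The pooled line can overstate what happened on drug. And if no rule is set beforehand, late cases can be explained away as due to rescue once the results are known, which would understate it.

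**Working it through.** The plan states no figure for this point, so there is none to reproduce. The check is a reading of the window, followed by illustrative arithmetic.

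**1. Is the window open-ended?** Yes. SAP 7.6.2 sets no last visit, no limit after the last dose and no rule for patients who start another antifungal.

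**2. How many scheduled tests fall after EOST?** Count twice-weekly visits, plus EOST, plus two follow-up visits:
- 14-day course: 4 + 1 + 2 = 7; 2/7 = 29%
- 28-day course: 8 + 1 + 2 = 11; 2/11 = 18%
- 42-day course: 12 + 1 + 2 = 15; 2/15 = 13%

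These shares apply to patients who attend both follow-up visits. For patients who fail and are rescued, Protocol 4.4 names only a 4-week safety assessment and does not spell out its content.

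**3. Can other planned outputs separate the timing?** The shift tables in 7.6.2 are by visit and use bands cut at ULN, 2x, 3x and 5x ULN.
- Approximately covered (6 of 14 rows): ALT and AST at 3x and 5x, total bilirubin at 2x, ALP at 2x. Some boundaries differ (at or above versus strictly above).
- Not covered (8 of 14 rows): ALT and AST at 10x (2), bilirubin and ALP at 1.5x (2), ALT or AST at 3x (1), aminotransferase plus bilirubin (2), potential Hy's Law (1).
- In every row, the follow-up columns mix rescued and non-rescued patients. Separating them means matching the laboratory and medication listings by hand.

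**4. What does one patient weigh?** 1/15 = 6.7 percentage points. If two patients meet a threshold and one does so only after EOST, the pooled line is 2/15 = 13.3% (exact 95% CI 1.7–40.5) and the on-treatment line is 1/15 = 6.7% (0.2–31.9). The SAP plans no interval for these counts; they are shown only to convey precision.

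**5. How many patients might be affected?** The documents give no failure, rescue or liver-event rate. Assume f of 15 patients fail and receive another antifungal, each with independent chance q of first crossing a threshold only after EOST. Expected number = f × q; chance of at least one = 1 − (1 − q)^f.

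| f (assumed) | q (assumed) | Expected patients | Points of 15 | Chance of at least one |
|---|---|---|---|---|
| 2 | 5% | 0.1 | 0.7 | 10% |
| 4 | 10% | 0.4 | 2.7 | 34% |
| 8 | 30% | 2.4 | 16.0 | 94% |

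The range is wide because both inputs are assumptions. It shows what could happen and is not an estimate.

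**The case against.** The strongest case for leaving the text alone has four parts.

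- **Including follow-up visits is sound.** It captures delayed injury, and for a safety screen an over-count is the cautious error. This stands, and it is why the pooled line should stay.
- **Other outputs exist.** There are by-visit summaries, shift tables, a listing of patients with abnormal liver tests, full laboratory listings and medication listings (SAP 7.3.6 and 7.6.2). Clinically significant laboratory abnormalities are also adverse events under Protocol 8.1, so they enter the during/after overview. This stands in part. The eight rows above are still not separated, the adverse-event route depends on the investigator's judgement of significance, and the overview is not organised by threshold. At about 15 patients the listings can be worked through case by case, but by no pre-specified rule.
- **Rescue is permitted, not required.** This stands. It is not known how many patients will be on another antifungal at the follow-up tests.
- **Nothing in the SAP calls these counts effects of APX001.** This stands. A reader might infer that abnormalities arising on rescue drugs are reported as APX001 results. The documents do not support that: these are descriptive counts in the Safety Population, and relatedness is assessed through drug-related adverse events. Nor do they support assuming that every crossing after rescue is caused by the rescue drug.

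**Conclusion.** The point holds in a limited form. The liver-threshold counts, including the combined and potential Hy's Law rows, have no on-treatment window, and the timing split used for adverse events is missing. Existing outputs repair this only in part. No efficacy result is affected and no planned analysis fails.

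The size is unknown. It is 6.7 points per affected patient at n = 15; any expected number rests on assumed rates. This is a cheap improvement to make before database lock.

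A reader might also conclude that cases first crossing a threshold after another antifungal should be left out of the liver-safety statement. They should not. If APX001 is stopped for a rising ALT and another antifungal is started, the bilirubin or Hy's Law criterion may first be met afterwards. Leaving that patient out could hide an APX001 injury.

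**What to change.** In SAP 7.6.2:

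1. Keep the count over any post-baseline visit as the main line.
2. For each threshold add two mutually exclusive columns, by date of first post-baseline crossing: (i) during the treatment period; (ii) after it.
3. Define the treatment period once, by dates, for both 7.6.1 and 7.6.2. Section 7.6.1 gives no date rule. Any lag after the last dose is for the sponsor to justify.
4. Within each column, flag patients whose first crossing came after another systemic antifungal was started, using dates from the concomitant-medication record. The flag sits inside the columns, so an antifungal started before the treatment period ends creates no overlap.
5. Report all columns in the liver-safety statement. Describe flagged cases as confounded and do not exclude them.

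Cost: SAP wording and derived timing and flag variables. Protocol 5.6.3 already collects medication start and stop dates throughout the study, and SAP 7.3.6 already identifies concomitant systemic antifungals, so no new data are needed. The downside is more columns with small counts.
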